The PLUNGER Stroke Trial

A comparison of cyclic manual direct aspiration thrombectomy (Plunger technique) vs. static manual direct aspiration thrombectomy for treatment of acute large vessel occlusion stroke with the Raptor Aspiration Catheter

Principle Investigator:

[name], PhD
Director of Vanderbilt Cerebrovascular Program
Associate Professor of Neurology and Neurosurgery
Vanderbilt University Medical Center
Nashville, TN

Study Summary

Title	A comparison of cyclic manual direct aspiration thrombectomy (Plunger technique) vs. static manual direct aspiration thrombectomy for treatment of acute large vessel occlusion stroke with the Raptor Aspiration Catheter
Short title	The Plunger Stroke Trial
Objective	To compare the efficacy and safety of cyclic manual direct aspiration thrombectomy (Plunger technique) vs static aspiration for direct aspiration thrombectomy with the Raptor Aspiration Catheter
Design	A randomized, controlled trial of the Plunger technique vs. static manual direct aspiration thrombectomy for treatment of acute large vessel occlusion stroke. At least one pass with aspiration is required.
Sample size	A sample size of 500 subjects will detect a 15% absolute difference in successful first pass rate between the two groups at 90% power.
Duration	With 20 sites, enrollment can be completed in one year (Sites to be decided)
Primary endpoint	First pass effect (FPE) defined as TICI 2c or 3 after the first attempt of direct aspiration thrombectomy
Safety endpoint	Rate of symptomatic intracranial hemorrhage (sICH)
Secondary endpoints	Overall rate of TICI 2b or 3 recanalization with Plunger vs. static aspiration Functional outcome at 90 days based on mRS assessment Rate of successful navigation of aspiration catheter to clot Rate of rescue treatment with stent-retrievers Rate of complete clot ingestion Recanalization rates with the two different sizes of Raptor Rate of recanalization by clot density on CT (hyperdense vs isodense)
Inclusion criteria	Acute ischemic stroke due to occlusion of the terminal ICA or M1 segment of the MCA Treatment can be initiated within 24 hours of symptom onset Age 18 years or older
Exclusion criteria	Evidence of acute intracranial hemorrhage prior to treatment Failure to obtain informed consent

Background

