A participant will be considered lost to follow-up for the secondary end-point, mRS, if he or she is unable to be contacted by the study site staff, either via telephone or an in-person meeting at 90-days after randomization. When all reasonable attempts to locate the subject have been exhausted, the subject will be considered lost to follow-up and their data will be excluded from the data analysis from the time of last contact onward. All data collected prior to last contact will be included in data analysis.

Statistical analysis

Sample size calculation

The true rate of successful FPE with aspiration thrombectomy can be estimated based on several prior studies. The COMPASS trial reported an 83% rate of TICI 2b or 3 after the first attempt with aspiration thrombectomy [4]. Similarly, Kang et al reported TICI 2b or 3 in 82% of patients after the first pass with aspiration thrombectomy [8], but that rate dropped to 19% when limiting the definition of successful FPE to TICI 2c or 3 [8]. Similarly, the ETIS investigators reported a 24% rate of TICI 3 FPE with the Sofia catheter [9]. Synthesizing these results, we estimate the predicted FPE (TICI 2c or 3) rate of static aspiration thrombectomy to be 25%.

While it is difficult to predict the treatment effect of the Plunger technique, our experience is that there is significantly more total clot ingestion with this technique. Total clot ingestion would be expected to particularly impact the TICI 2c/3 rate of FPE. Therefore, we estimate that the Plunger technique may increase FPE rate by 15% over static aspiration (predicted Plunger FPE of 40%).

A minimum sample size of 462 would be required to detect a difference of 15% between these two groups with 90% power at alpha of 0.05. Given that the actual FPE rates are difficult to estimate and accounting for inability to access the lesion with the Raptor and missing data, we plan for a total minimum sample size of 500.

Population for analysis

A modified intention-to-treat (mITT) analysis will be employed, wherein all subjects for whom navigation of the Raptor to the clot failed will be excluded from the subsequent ITT analyses. This is because those subjects will not be treated by either of the techniques being studied in this trial. Once navigation failures are excluded, the remainder of the population will be compared based on assigned treatment technique per randomization.

Analysis of primary effectiveness endpoint

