The primary endpoint is the first pass effect (FPE), defined as TICI 2c or 3 after the first attempt of direct aspiration thrombectomy, as determined by core lab assessment. The rate of successful FPE will be compared between the Plunger group and the static aspiration group per the mITT population as above.

Null hypothesis: the rate of successful FPE is not different between static and plunger aspiration. The rate of FPE will be compared between the two groups by chi-square analysis. If there is a significant difference between the two, then the null hypothesis will be rejected.

Analysis of primary safety endpoint

The primary safety endpoint is the rate of sICH at 24 hours compared between the static and Plunger aspiration groups. A chi-square test will assess for differences in rate of sICH between the two treatment groups in the mITT population. Secondary analyses will account for ASPECTs score and time to treatment between the two groups.

Analysis of secondary endpoints

Overall rate of TICI 2b or 3 recanalization with Plunger vs. static aspiration will also be compared using chi-square analysis on the mITT population.

For the following additional binomial secondary efficacy endpoints, treatment groups will be compared using logistic regression models as appropriate:

- Rate of successful navigation of aspiration catheter to clot
- Rate of rescue treatment with stent-retrievers
- Rate of complete clot ingestion
- Rate of recanalization by clot density on CT (hyperdense vs isodense)

The 90-day functional outcomes, including mRS and PROMIS-10, will be compared between the two groups using ordinal shift analysis.

Randomization

Patients will be randomized (1:1; permuted block randomization) once the decision is made for patient to go for thrombectomy using the REDCap randomization tool.

Adverse events

Throughout the course of the clinical investigation, all adverse events will be recorded on the applicable Adverse Event CRF. The date of onset, date of resolution, severity, and action taken will be evaluated by the Investigator. The relationship to the technique or device, relationship to the procedure, and clinical significance will be evaluated. The neurological outcomes and adverse events will be reported.

Adverse Event Classification and Definitions

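### The minimum sample size of 462 does not follow from the protocol's own inputs (25% vs 40%, 90% power, alpha 0.05), which give 406; the error is conservative

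*Protocol*

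**What the plan says.** The Sample size calculation section sets the control rate from earlier studies: "we estimate the predicted FPE (TICI 2c or 3) rate of static aspiration thrombectomy to be 25" per cent. It then adds 15 points for the Plunger technique ("predicted Plunger FPE of 40" per cent). The next paragraph gives the requirement, at alpha 0.05: "A minimum sample size of 462 would be required to detect a difference of 15% between these two groups with 90% power".

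The allowance for loss comes only after that figure. The target is raised to 500 with the reason "Given that the actual FPE rates are difficult to estimate and accounting for inability to access the lesion with the Raptor and missing data".

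The remaining inputs are elsewhere in the protocol. The Analysis of primary effectiveness endpoint section says "The rate of FPE will be compared between the two groups by chi-square analysis", under a null hypothesis of no difference. The Randomization section gives 1:1 allocation. The Study Summary says "A sample size of 500 subjects will detect a 15% absolute difference in successful first pass rate between the two groups at 90% power", without naming the rates.

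**The concern.** The two groups in the sample-size sentence are those that the preceding paragraphs predict at 25% and 40%. Power, alpha, test and allocation are all given, so a reader should be able to recover 462, and cannot. This is the only sample-size calculation in the protocol.

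The practical stake is the margin for loss. The primary analysis uses a modified intention-to-treat population that leaves out patients in whom the Raptor could not be navigated to the clot, and the protocol gives no expected rate for that or for missing data. Someone who takes 462 as the floor would conclude that 90% power is lost once more than 38 of 500 patients (7.6%) are not evaluable. Under the protocol's own rates the margin is more than twice as wide.

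**Working it through.** **Inputs.** p1 = 0.25 and p2 = 0.40, difference d = 0.15, power 0.90, alpha 0.05 (Sample size calculation); chi-square test with a null of no difference, read as two-sided (Analysis of primary effectiveness endpoint); 1:1 allocation (Randomization). Sidedness is the only inferred input, so one-sided is also tried. The mean rate is p̄ = 0.325.

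**Requirement for the uncorrected chi-square test.**

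n per arm = [1.960·√(2p̄(1−p̄)) + 1.2816·√(p1(1−p1) + p2(1−p2))]² / d²

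- √(2 × 0.325 × 0.675) = 0.6624, and 1.960 × 0.6624 = 1.2983
- √(0.1875 + 0.2400) = 0.6538, and 1.2816 × 0.6538 = 0.8379
- n = (1.2983 + 0.8379)² / 0.0225 = 4.563 / 0.0225 = 202.8, so 203 per arm and **406 in total**

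Exact enumeration gives the chi-square test 90.1% power at 203 per arm.

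**Attempts to reach 462 with other usual methods, same inputs.**

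| Method | Per arm | Total |
|---|---|---|
| Unpooled variance | 200 | 400 |
| Arcsine | 203 | 406 |
| Simple pooled variance | 205 | 410 |
| Continuity-corrected | 216 | 432 |
| Fisher's exact, by enumeration (90.1% power; 89.8% at 214 per arm) | 216 | 432 |
| One-sided 0.05, uncorrected | 166 | 332 |

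**Attempts with the other rates the protocol cites, 15-point gap kept.** One source is reported as "that rate dropped to 19% when limiting the definition of successful FPE to TICI 2c or 3"; a control rate of 19% needs 360. Another reported 24%, which needs 400. Both are further from 462.

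**What would give 462.** Each of these needs an input that the protocol does not state or that it contradicts:

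- a 15-point gap at a control rate of 39–46% (462 to 464; the maximum over all control rates is 464);
- 2:1 allocation (154 + 308 = 462), against the stated 1:1;
- 12% loss already included (406 / 0.88 = 461.4, so 462), although the allowance for loss is described as the step from 462 to 500.

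**Size of the gap.** 462 − 406 = 56 (56/406 = 14%). 462 − 432 = 30 (30/432 = 7%).

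**Power at 25% vs 40%.** Power = Φ[(d√n − 1.2983) / 0.6538].

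- 231 per arm (462): (2.2798 − 1.2983) / 0.6538 = 1.501, so 93.3% (exact 93.5%; Fisher 92.1%)
- 250 per arm (500): (2.3717 − 1.2983) / 0.6538 = 1.642, so 95.0% (exact 95.0%)

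**Margin for loss, 500 randomised, equal loss in both arms.** (500 − 406)/500 = 94/500 = 18.8%. On the continuity-corrected basis, (500 − 432)/500 = 68/500 = 13.6%. The protocol gives no loss rate, so these are assumed values, for the uncorrected test:

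| Assumed loss | Evaluable | Power |
|---|---|---|
| 5% | 475 | 93.9% |
| 10% | 450 | 92.7% |
| 15% | 425 | 91.3% |
| 20% | 400 | 89.6% |

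**The case against.** The strongest defence is that the 462 sentence names a difference of 15%, not the two rates, so the two groups could simply mean the two arms. A 15-point gap is hardest to detect near 50%, where it needs at most 464. On that reading 462 is close to a worst case that does not depend on the control rate, and the fault is an unstated assumption rather than wrong arithmetic. This is a possible origin, but the text does not support it: the sentence directly follows the predictions of 25% and 40%, and uncertainty about the rates is given as a reason for going from 462 to 500, not as something already inside 462.

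A second objection is that the harm is small. That stands. The figure errs on the safe side, and the enrolment target, test and population do not change.

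A third is that the adequacy of 500 is conditional, and this also stands. The protocol gives no rate for navigation failure or missing data, so nobody can confirm that loss stays under 18.8%. If the true rates were the least favourable for a 15-point gap (42.5% vs 57.5%), 500 evaluable would give 92.1% power, but an assumed 10% loss would bring that to 89.2%. The Study Summary statement is therefore safe at every control rate only if nearly all 500 are evaluable.

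**Conclusion.** The concern holds. From 25% vs 40%, 90% power, two-sided alpha 0.05, 1:1 allocation and a chi-square test, the requirement is 406 evaluable patients, or 432 with a continuity correction. The stated 462 exceeds these by 14% and 7%, which is more than rounding or choice of software can explain.

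It is an error of statement, not a threat to the trial: under its stated rates the trial has more power than it claims. A planned 500 is sufficient at those rates provided that no more than 18.8% of patients (13.6% with correction) are not evaluable and that loss is about equal in the two arms. The point should be fixed, at low priority.

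**What to change.** Replace the sentence giving 462 with one that states its inputs and a single basis. For the uncorrected test:

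> With FPE rates of 25% and 40%, a two-sided chi-square test at 0.05 and 1:1 allocation, 406 evaluable patients (203 per arm) give 90% power. Randomising 500 gives about 95% power if all are evaluable and keeps 90% with up to 18.8% not evaluable.

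If the test will be continuity-corrected, use 432 (216 per arm), 93.9% power at 500 and a limit of 13.6% instead. State the expected combined rate of navigation failure and missing data, so that the limit can be compared with it.

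If 462 was meant to cover a control rate of about 39–46%, keep it but name those rates and call it a worst case. In the Study Summary, add the assumed rates and the evaluable number so that the two places agree.

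The cost is one sentence and one clause, with no change to enrolment, test or analysis population.

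### The only stated analysis population drops every Raptor navigation failure, which would empty the navigation-success comparison and remove part of the stent-retriever rescue endpoint

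*Protocol*

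**What the plan says.** **The population.** Under Population for analysis, the Protocol sets a modified ITT (mITT) in which "all subjects for whom navigation of the Raptor to the clot failed will be excluded from the subsequent ITT analyses". The reason given is: "This is because those subjects will not be treated by either of the techniques being studied in this trial". The section ends: "Once navigation failures are excluded, the remainder of the population will be compared based on assigned treatment technique per randomization". No other analysis population is named in the document.

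**Analyses labelled mITT.** There are three:
- first pass effect, compared "per the mITT population as above";
- symptomatic intracranial hemorrhage, compared "between the two treatment groups in the mITT population";
- overall TICI 2b or 3, which "will also be compared using chi-square analysis on the mITT population".

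**Analyses with no label.** The next sentence under Analysis of secondary endpoints reads: "For the following additional binomial secondary efficacy endpoints, treatment groups will be compared using logistic regression models as appropriate". The list below it opens with "Rate of successful navigation of aspiration catheter to clot". It continues with stent-retriever rescue, complete clot ingestion, and recanalization by clot density. The list names no population and makes no exception to the exclusion.

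**The rescue endpoint.** Under Objective and endpoints, Secondary endpoints, stent-retriever rescue covers two situations: use after at least one aspiration attempt, and use when the Raptor could not be brought to the clot.

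**Timing.** Under Randomization, patients are randomized when the decision for thrombectomy is made. A patient with failed navigation is therefore already randomized to an arm.

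**The concern.** The exclusion rule is general, and all endpoint analyses come after it in the text. Two listed endpoints depend on the patients it removes. Navigation success has failures only among those patients. Stent-retriever rescue takes one of its two described sources of events from them.

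An analyst who follows the Protocol's only stated population gets an empty comparison for the first endpoint. For the second, the analyst gets a result that looks complete and is not. The first problem would be noticed at once because the model fails. The second could pass unnoticed because the model runs normally. An analyst who uses all randomized patients instead gets sensible results, but departs from the only population the Protocol defines. That choice should be written down before outcome data are seen.

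**Working it through.** The Protocol gives no navigation-failure or rescue figure, so there is no stated result to reproduce. The check is to apply the stated rule to each endpoint.

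**Step 1: navigation success under the mITT.** Let n be the number of patients in an arm whose Raptor reached the clot. The mITT keeps only those n, so the success rate is n/n = 100% in each arm and the difference is 0 by construction. As a check, a logistic model was fitted to 462 patients (231 per arm), all with success. It failed with a singular matrix, as it must when the outcome is constant.

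**Step 2: navigation success in all randomized patients.** The planned total is 500 with 1:1 allocation, so 250 per arm. The failure rate f is an assumption. Three values are shown, equal in both arms:

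| Assumed f | Failures of 500 | Success rate | 95% CI half-width for the difference |
|---|---|---|---|
| 2% | 10 | 98.0% | 2.45 points |
| 7.6% | 38 | 92.4% | 4.65 points |
| 15% | 75 | 85.0% | 6.26 points |

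Half-width = 1.96 × √(2f(1 − f)/250). For f = 0.076: 1.96 × √(2 × 0.076 × 0.924/250) = 1.96 × 0.0237 = 0.0465.

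The 7.6% is (500 − 462)/500, the whole sample-size margin. Sample size calculation assigns that margin jointly to uncertain first-pass rates, lesion access and missing data, so it is a scenario and not a stated failure rate. At that value, with 231 of 250 successes per arm, the logistic model gives an odds ratio of 1.00 (95% CI 0.52 to 1.94), so the comparison can be estimated. The half-widths show how precise the repaired analysis would be. They do not measure an error in the plan.

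**Step 3: stent-retriever rescue.** In one arm, let r be the rescue rate among patients whose Raptor reached the clot, f the navigation-failure rate, and g the share of navigation failures who receive a stent-retriever.
- mITT rate: r
- All-randomized rate: (1 − f)r + fg = r + f(g − r)
- Difference between the two: f(g − r)

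The mITT drops the fraction fg of randomized patients who had a rescue that the endpoint description counts. The Protocol gives none of f, g and r, so neither the shift within an arm nor its effect on the between-arm comparison can be calculated. Since g and r lie between 0 and 1, the shift within an arm cannot exceed f.

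**Step 4: the other two listed endpoints.** Complete clot ingestion and recanalization by clot density presuppose an aspiration attempt, so the mITT suits them. The list therefore mixes endpoints that need different denominators, and one label for the whole list would not solve the problem.

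**The case against.** The strongest reply is that the Protocol never says these two endpoints use the mITT. It attaches that label to three analyses and leaves it off the list that follows. The reason given for the exclusion concerns patients who receive neither technique. That bears on technique outcomes and not on navigation, which is settled before aspiration starts. Navigation success is collected for every procedure (Data collection, Schedule of assessments), and failures receive narrative reports (Adverse Event Classification and Definitions). An analyst is unlikely to delete all failures and then model success. The population for each secondary endpoint is also commonly left to the SAP.

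Much of this stands. A reader might infer that the Protocol prescribes an impossible analysis outright. It does not: the conflict arises only if the general rule is applied, and all randomized patients may have been intended. What remains is that the rule is general, no exception is written, and an SAP would have to choose between following it and departing from it. The rescue wording may only describe when rescue is used and not fix a denominator, and an mITT rescue rate is a legitimate quantity. It is still narrower than the endpoint as described.

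A reader might also infer a second contradiction. The navigation endpoint refers to the aspiration catheter while the exclusion refers to the Raptor, and Navigation technique allows other catheters after Raptor failure. The documents do not support giving this much weight. The Secondary endpoints section uses the two terms interchangeably in neighbouring bullets, use of another catheter is treated as a protocol deviation, and the Data collection list is a summary and not the case report form. It merits a wording clarification only.

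Nor does the population conflict show a fault in the primary or safety analysis. Both are explicitly assigned to the mITT and can be run there.

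**Conclusion.** The point holds in conditional form. The Protocol's one stated population excludes every randomized patient in whom the Raptor could not be navigated to the clot, and no exception is made for two endpoints that depend on those patients. If the rule is applied, navigation success is 100% in both arms and cannot be compared. Stent-retriever rescue can still be estimated but leaves out the navigation-failure rescues. The first consequence follows from the definitions and needs no assumed rate. The size of the second cannot be derived from the document.

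The conflict is confined to secondary endpoints, and the underlying data are already to be collected. It should be corrected, but it does not threaten the trial's main conclusion.

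**What to change.** 1. In Population for analysis and in Analysis of secondary endpoints, state that navigation success and stent-retriever rescue are analysed in all randomized patients by assigned arm. Keep the mITT for endpoints that need an aspiration attempt.
2. Report the number of navigation failures by arm, so that readers can see whether the post-randomization exclusion was balanced.
3. As a minor clarification, name the Raptor in the navigation endpoint wherever it appears (Secondary endpoints, Data collection, Analysis of secondary endpoints), so that it matches the exclusion. The same yes/no item determines who belongs to the mITT, so it should have one meaning.

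The cost is a few sentences, a clearer label on an existing data item, and a slightly broader denominator for two secondary endpoints. No new data are needed: navigation success and the rescue device are already on the procedure list.

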Patients with a large vessel occlusion who are clinically appropriate for thrombectomy will be screened for participation. Subjects who meet selection criteria below will be enrolled. Note that there are no parenchymal imaging criteria; site investigators will determine if individual patients will benefit from thrombectomy. The trial is not intended to assess clinical criteria for endovascular treatment decisions, but rather to assess *technique* of thrombectomy once that decision has been made.

Inclusion criteria

1. Acute ischemic stroke due to occlusion of the terminal ICA or M1 segment of the MCA
2. Treatment can be initiated within 24 hours of onset
3. Age of 18 years or older

Exclusion criteria

Evidence of acute intracranial hemorrhage prior to treatment

Failure to obtain informed consent

Subject withdrawal

Subjects enrolled in the study can discontinue their participation at any time for any reason without prejudice or reduction in the quality of their medical care. The investigator can terminate a subject's participation in the study to protect the subject's health. The Investigator must document this notification of withdrawal from the study in the appropriate CRF and notify the sponsor.

Data collection

Baseline data: At the time of endovascular treatment, the following data will be collected for all subjects:

- Age
- Baseline mRS
- ASPECTS score
- Hyperdense vessel sign (yes/no; site-reported)
- NIHSS
- Location of occlusion (right or left, ICA terminus or M1)

Procedure data: The following will be collected immediately after the procedure:

- Guide catheter used
- Which Raptor used (0.071" or 0.074")
- Microcatheter used (Carrier or other)
- Microwire used
- Successful navigation? (yes/no)

- Total duration of aspiration
- Total duration of plunging (if assigned to Plunger technique)
- Reperfusion (TICI) after each pass (site-assessed)
- Clot ingestion: none, partial, or complete
- Groin puncture time
- On-clot time
- Time of reperfusion
- Rescue treatment? If yes, what device and how many passes

24 hour data: To be collected at 24 hrs post-procedure +/- 6 hours:

- Imaging evidence of hemorrhage? If parenchymal, HI1, HI2, PH1, or PH2; or IVH, SAH, SDH
- Symptomatic ICH?
- NIHSS

90 day follow up: To be collected by phone at 90 days +/- 30 days

- Modified Rankin Score

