- PROMIS-10 score (a publically available global health assessment tool that allows measurements of symptoms, functioning, and healthcare-related quality of life for a wide variety of chronic diseases and conditions.

Telephone follow up

Telephone follow-up will be conducted where information related to the subject's mRS assessment and Quality of Life assessment will be collected. If the subject is unavailable for any reason, the subject's family/relative or caregiver/LAR will be requested to provide the applicable information.

Schedule of assessments

	Baseline	Procedure	24 hours Post Procedure	90 days Post Procedure (telephone)
Eligibility	♦			
Demographics and Medical History	♦			
Location of occlusion	♦			
mRS Assessment	♦			♦
NIHSS Assessment	♦		♦	

Head CT: ASPECTS, hyperdense vessel, hemorrhage	♦		♦	
Devices used		♦		
Successful navigation		♦		
Time of aspiration, plunging, and time to reperfusion		♦		
Reperfusion score (TICI; site-assessed and core lab)		♦		
Rescue treatment, if applicable		♦		
Clot ingestion		♦		
PROMIS-10				♦
Adverse Events		♦	♦	♦

Recording data

Study data will be collected using electronic case report forms and a electronic data capture system (REDCap). The system allows the capability of data collection remotely through the internet so the participating clinical site personnel may log on to the system securely and enter the data. All subjects' data collected in the system will be extensively verified through data validation programs, database integrity rules, and investigation-specific data entry conventions for data accuracy and logical meaningfulness. Periodic analysis of all subjects' data collected will be performed in order to examine the expected distributions of data and to identify outliers for possible data entry errors.

The Investigator is responsible for reviewing all eCRF entries for completion and correctness. Changes in case report forms will be made electronically and the system used will keep an audit trail of changes. If necessary, an explanation for the change(s) may be provided. The Investigator will electronically approve all eCRF data.

All study staff that enter data into eCRFs will undergo appropriate training for use of eCRFs.

Loss to Follow-up

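### The primary first-pass test is fixed as an unadjusted chi-square, although two baseline factors already collected could add a little precision at almost no cost

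*Protocol*

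**What the plan says.** The Protocol fixes the primary comparison in Analysis of primary effectiveness endpoint: "The rate of FPE will be compared between the two groups by chi-square analysis". The decision rule follows directly: "If there is a significant difference between the two, then the null hypothesis will be rejected". The population is the modified intention-to-treat set, and no covariate or stratification factor is named for this test.

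Data collection, Baseline data, opens with "At the time of endovascular treatment, the following data will be collected for all subjects". The list includes "Hyperdense vessel sign (yes/no; site-reported)" and "Location of occlusion (right or left, ICA terminus or M1)". The Schedule of assessments has a row "Head CT: ASPECTS, hyperdense vessel, hemorrhage", marked at baseline and at 24 hours.

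Under Randomization, "Patients will be randomized (1:1; permuted block randomization) once the decision is made" for thrombectomy. No stratifier is stated.

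Clot density is not ignored. Analysis of secondary endpoints lists "Rate of recanalization by clot density on CT (hyperdense vs isodense)" among the endpoints for logistic regression. In the endpoint list, the Protocol explains that hyperdense clot is thought to be softer and easier to remove, and adds that this has not been studied for aspiration. Covariates are also foreseen for secondary analyses of symptomatic haemorrhage (ASPECTS and time to treatment).

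**The concern.** Without stated stratification, balance on the hyperdense sign and the occlusion site is left to chance. The unadjusted test treats any outcome variation due to these factors as noise. If either factor predicts FPE, adjustment removes that part of the variance and the same patients give a slightly more precise comparison. If neither does, adjustment for two binary factors costs almost nothing at this sample size.

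The point belongs at protocol level because the Protocol itself names the primary test and ties rejection of the null hypothesis to it. An analysis plan could add an adjusted analysis, but making it primary would depart from the Protocol text. The gain is credible only if the method is fixed before outcome data are seen.

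The stake is modest. The Protocol calls the FPE rates hard to estimate and the treatment effect hard to predict. A true effect below 15 points would take power well below 90%, and there a little extra precision is worth somewhat more.

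**Working it through.** **Inputs from the Protocol (Sample size calculation).** FPE 25% static and 40% Plunger; 90% power; alpha 0.05, taken as two-sided because the null hypothesis is one of no difference; minimum 462 and planned 500 patients, 1:1.

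**The plan's own figure.** The standard two-sided formula with pooled variance gives

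n per arm = [1.96·√(2·0.325·0.675) + 1.2816·√(0.25·0.75 + 0.40·0.60)]² / 0.15² = 202.8, so 203 per arm and 406 in total.

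With continuity correction the total is 432. The stated 462 is not reproduced and is on the safe side. That is a separate matter. Its consequence here is that the starting power is 93.3% at 462 and 95.0% at 500.

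**Assumptions (not in the documents).**
- Half of patients have the hyperdense sign; a quarter have an ICA terminus occlusion; the two are independent.
- FPE differs by 8, 14 or 20 points by sign (dh) and by 5, 10 or 15 points by site (ds): weak, middle, strong.

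**Variance explained.** R² = [dh²·0.25 + ds²·0.1875] / mean of p(1−p) over the arms. For 25%/40% the denominator is (0.1875 + 0.24)/2 = 0.21375.
- Weak: (0.0016 + 0.00047)/0.21375 = 0.97%
- Middle: (0.0049 + 0.001875)/0.21375 = 3.17%
- Strong: (0.0100 + 0.00422)/0.21375 = 6.65%

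**Power.** Φ((d − 1.96·SE0)/SE1), where SE0 is pooled, SE1 is unpooled, and both are multiplied by √(1−R²). At 462 without adjustment, SE0 = 0.04358 and SE1 = 0.04302, so (0.15 − 0.0854)/0.04302 = 1.50, which gives 93.3%. Patient equivalent = 462/(1−R²) − 462.

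| Setting | Unadjusted | Weak | Middle | Strong |
|---|---|---|---|---|
| 25% vs 40%, N=462 | 93.3% | 93.6% | 94.0% | 94.8% |
| 25% vs 40%, N=500 | 95.0% | 95.2% | 95.6% | 96.2% |
| 25% vs 35%, N=462 | 65.1% | 65.5% | 66.5% | 68.2% |
| Patients gained on 462 (25% vs 40%) | – | 5 | 15 | 33 |

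The 25% vs 35% row is an assumed smaller effect; its denominator is 0.2075.

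**Hyperdense sign alone**, the only factor with a rationale in the Protocol: R² = 0.7%, 2.3% or 4.7%; power at 462 is 93.5%, 93.8% or 94.4%; about 4 (3.5), 11 or 23 patients.

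**Misreading by sites.** A misreading rate m multiplies dh by (1−2m). Both factors together are then worth about 3, 11 or 24 patients at m = 10%, and 2, 8 or 18 at m = 20%.

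**Simulation** (100,000 trials per setting, 25% vs 40%, N=462):

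| Method | Weak | Middle | Strong |
|---|---|---|---|
| Chi-square | 93.5% | 93.4% | 93.5% |
| Cochran-Mantel-Haenszel, four strata | 93.5% | 93.8% | 94.7% |
| Standardised risk difference | 93.7% | 94.1% | 94.9% |

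For 25% vs 35%, chi-square gives 65.2/65.5/65.3% and Cochran-Mantel-Haenszel 65.3/66.4/67.9%. With no prognostic value, power for 25% vs 40% is 93.5% (chi-square), 93.3% (Cochran-Mantel-Haenszel) and 93.6% (risk difference). Type I error is 4.9–5.1% for the first two and 5.1–5.3% for the risk difference, whose 95% interval covers 94.6–94.9%. A small part of the risk-difference gain is therefore excess type I error, and Cochran-Mantel-Haenszel is the like-for-like comparison with the chi-square.

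**Second parameterisation.** With the same odds ratio for each factor, in opposite directions, at N=500, the closed-form gain is about 2, 7, 21 and 50 patients for odds ratios of 1.25, 1.5, 2 and 3. Simulated Cochran-Mantel-Haenszel power is 95.3%, 95.6% and 96.4% at odds ratios 1.5, 2 and 3, against about 95.0% for chi-square. The conclusion is the same.

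**The case against.** The strongest case against is that nothing is broken. An unadjusted chi-square is an ordinary, valid test for this randomisation, and an unseen analysis plan may add adjusted analyses. Power already exceeds 90% under the Protocol's assumptions. Every input that drives the gain is assumed: the Protocol says the density relation has not been assessed for aspiration, and it offers no evidence that site predicts FPE. The strong case needs a 20-point covariate effect, larger than the 15-point treatment effect. In the weak case the stratified test gains nothing. The outcome is read blind by a core lab, whereas the sign is reported by sites, possibly once the arm is known, so adjustment brings a softer input into the primary result.

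Most of this stands and limits the point to an optional improvement. Two parts do not remove it. The Protocol, not an unseen plan, fixes the primary test. The worry about the site-reported sign is met by recording it from the pre-treatment scan before the procedure, preferably before randomisation.

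One further objection is fair: the Baseline data list has the sign and the 24-hour list does not, so the shared head CT row in the schedule is only a minor ambiguity. Stating which scan is meant is a clarification.

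**Conclusion.** The point holds as a small efficiency gain to consider, not as an error. For the planned 25% vs 40% at 462 patients, like-for-like simulation gives about 0, 0.4 or 1.2 power points under weak, middle or strong covariates; the closed form puts this at about 5, 15 or 33 patients. For 25% vs 35% the like-for-like gain is 0.1, 0.9 or 2.6 points, and power stays below 70%. If neither factor is prognostic, the loss is about 0.2 points at most.

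These figures rest on the assumed prevalences and covariate effects. The Protocol supports only clot density, and only by rationale. Misreading of the sign reduces the gain. The 90% target for 25% vs 40% is met with or without the change.

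**What to change.** Before any outcome data are seen, replace the primary FPE test with one of the following, on assigned arm in the stated analysis population:
- a Cochran-Mantel-Haenszel test over the four strata of hyperdense sign (yes/no) by site (ICA terminus/M1), the option with type I error closest to nominal; or
- a standardised risk difference with 95% confidence interval from a logistic model with arm, sign and site. This keeps the overall difference in FPE rates as the effect measure, which a conditional odds ratio would not.

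Name one as primary and keep the chi-square as a sensitivity analysis. Add three short rules:
- The sign is the reading of the pre-treatment CT.
- Sign and site are entered before the procedure, preferably before randomisation.
- Missing baseline values are handled simply, for example with a separate not-recorded category.

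The cost is Protocol and analysis-plan wording, slightly earlier entry of two existing fields in an acute setting, and little extra analysis work. No new data are needed. The downside is that the primary analysis would then use a site-reported covariate.
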